**Table 9 Highly Effective Contraceptive Methods**

Highly Effective Contraceptive Methods That Are User Dependent a Failure rate of <1% per year when used consistently and correctly.
Combined (estrogen- and progestogen-containing) hormonal contraception associated with inhibition of ovulation b 
 
• oral
 
• intravaginal
 
• transdermal
 

Progestogen-only hormonal contraception associated with inhibition of ovulation b 
 
• injectable
 

Highly Effective Methods That Are User Independent

 
• Implantable progestogen-only hormonal contraception associated with inhibition of ovulationb
 
• Intrauterine device (IUD)
 
• Intrauterine hormone-releasing system (IUS)
 
• bilateral tubal occlusion
 

Vasectomized partner  (A vasectomized partner is a highly effective contraception method provided that the partner is the sole male sexual partner of the WOCBP and the absence of sperm has been confirmed. If not, an additional highly effective method of contraception should be used.)
Sexual abstinence  (Sexual abstinence is considered a highly effective method only if defined as refraining from heterosexual intercourse during the entire period of risk associated with the study drug. The reliability of sexual abstinence needs to be evaluated in relation to the duration of the study and the preferred and usual lifestyle of the participant.)

## NOTES:

- Typical use failure rates may differ from those when used consistently and correctly. Use should be consistent with local regulations regarding the use of contraceptive methods for participants in clinical studies.
- Hormonal contraception may be susceptible to interaction with the study drug, which may reduce the efficacy of the contraceptive method. In this case two highly effective methods of contraception should be utilized during the treatment period and for at least 90 after the last dose of study treatment

## **Collection of Pregnancy Information**

### **Male participants with partners who become pregnant**

- Investigator will attempt to collect pregnancy information on any male participant's female partner of a male study participant who becomes pregnant while participating in this study. This applies only to participants who receive study treatment.
- After obtaining the necessary signed informed consent from the pregnant female partner directly, the investigator will record pregnancy information on the appropriate form and submit it to GSK within 24 hours of learning of the partner's pregnancy.
- Partner will also be followed to determine the outcome of the pregnancy. Information on the status of the mother and child will be forwarded to GSK.
- Generally, follow-up will be no longer than 6 to 8 weeks following the estimated delivery date. Any termination of the pregnancy will be reported regardless of fetal status (presence or absence of anomalies) or indication for procedure.

### 13.6. Appendix 6: Liver Safety Required Actions and Follow up Assessments

#### Phase I liver chemistry stopping criteria and required follow up assessments

Liver Chemistry Stopping Criteria	
ALT-absolute	
ALT<math>\geq</math>3xULN
 
If ALT<math>\geq</math>3xULN AND bilirubin <math>\geq</math> 2xULN (>35% direct bilirubin) or INR >1.5, Report as an SAE.
 
See additional Actions and Follow Up Assessments listed below

Required Actions and Follow up Assessments	
Actions	Follow Up Assessments

 
• Immediately discontinue study treatment
 
• Report the event to GSK within 24 hours
 
• Complete the liver event CRF, and complete an SAE data collection tool if the event also meets the criteria for an SAE
 
• Perform liver event follow up assessments
 
• Monitor the subject until liver chemistries resolve, stabilise, or return to within baseline (see MONITORING below)
 
 
MONITORING:
 
If ALT<math>\geq</math>3xULN AND bilirubin <math>\geq</math> 2xULN or INR >1.5
 
 
• Repeat liver chemistries (include ALT, AST, alkaline phosphatase, bilirubin) and perform liver event follow up assessments within 24 hrs
 
• Monitor subjects twice weekly until liver chemistries resolve, stabilise or return to within baseline
 
• A specialist or hepatology consultation is recommended
 
 
If ALT<math>\geq</math>3xULN AND bilirubin < 2xULN and INR <math>\leq</math>1.5:
 
 
• Repeat liver chemistries (include ALT, AST, alkaline phosphatase, bilirubin) and perform
 
	
 
• Viral hepatitis serology
 
• Obtain INR and recheck with each liver chemistry assessment until the transaminases values show downward trend
 
• Obtain blood sample for pharmacokinetic (PK) analysis, obtained within 24 hours of last dose
 
• Serum creatine phosphokinase (CPK) and lactate dehydrogenase (LDH).
 
• Fractionate bilirubin, if total bilirubin<math>\geq</math>2xULN
 
• Obtain complete blood count with differential to assess eosinophilia
 
• Record the appearance or worsening of clinical symptoms of liver injury, or hypersensitivity, on the AE report form
 
• Record use of concomitant medications on the concomitant medications report form including acetaminophen, herbal remedies, other over the counter medications.
 
• Record alcohol use on the liver event alcohol intake case report form
 
 
If ALT<math>\geq</math>3xULN AND bilirubin <math>\geq</math> 2xULN or INR >1.5:
 
 
• Anti-nuclear antibody, anti-smooth muscle
 

Liver Chemistry Stopping Criteria	

liver event follow up assessments within 24-72 hrs
 
 
• Monitor subjects weekly until liver chemistries resolve, stabilize or return to within baseline
 
	
antibody, Type 1 anti-liver kidney microsomal antibodies, and quantitative total immunoglobulin G (IgG) or gamma globulins.
 
 
• Serum acetaminophen adduct high performance liquid chromatography (HPLC) assay (quantifies potential acetaminophen contribution to liver injury in subjects with definite or likely acetaminophen use in the preceding week [James, 2009]. NOTE: not required in China.
 
• Liver imaging (ultrasound, magnetic resonance, or computerised tomography) and /or liver biopsy to evaluate liver disease; complete Liver Imaging and/or Liver Biopsy CRF forms.
 

1. Serum bilirubin fractionation should be performed if testing is available. If serum bilirubin fractionation is not immediately available, discontinue study treatment for that subject if ALT  $\geq$  3xULN and bilirubin  $\geq$  2xULN. Additionally, if serum bilirubin fractionation testing is unavailable, record presence of detectable urinary bilirubin on dipstick, indicating direct bilirubin elevations and suggesting liver injury.
2. All events of ALT  $\geq$  3xULN and bilirubin  $\geq$  2xULN (>35% direct bilirubin) or ALT  $\geq$  3xULN and INR>1.5, if INR measured, which may indicate severe liver injury (possible 'Hy's Law'), must be reported as an SAE (excluding studies of hepatic impairment or cirrhosis); INR measurement is not required and the threshold value stated will not apply to subjects receiving anticoagulants
3. Includes: Hepatitis A, immunoglobulin M (IgM) antibody; Hepatitis B surface antigen and Hepatitis B Core Antibody; Hepatitis C ribonucleic acid (RNA); Cytomegalovirus IgM antibody; Epstein-Barr viral capsid antigen IgM antibody (or if unavailable, obtain heterophile antibody or monospot testing); Hepatitis E IgM antibody
4. PK sample may not be required for subjects known to be receiving placebo or non-GSK comparator treatments. Record the date/time of the PK blood sample draw and the date/time of the last dose of study treatment prior to PK blood sample draw on the CRF. If the date or time of the last dose is unclear, provide the subject's best approximation. If the date/time of the last dose cannot be approximated OR a PK sample cannot be collected in the time period indicated above, do not obtain a PK sample. Instructions for sample handling and shipping are in the SRM.

**13.7. Appendix 7: Protocol Amendment History**

The Protocol Amendment Summary of Changes Table for the current amendment is located directly before the Table of Contents (TOC).

## 1. INTRODUCTION

The purpose of this reporting and analysis plan (RAP) is to describe the analyses to be included in the Clinical Study Report for Protocol 205021:

Revision Chronology:		
2017N322016_00	06-OCT-2017	Original
2017N322016_01	17-OCT-2017	Original Protocol Republishing
2017N322016_02	24-JUL-2018	Formulation change to enteric capsule

## 2. SUMMARY OF KEY PROTOCOL INFORMATION

### 2.1. Changes to the Protocol Defined Statistical Analysis Plan

This study was terminated during Cohort 2 of Part A. Participants in Cohort 2 received only 2 of 4 planned single doses.

Changes from the originally planned statistical analysis specified in the protocol are outlined in [Table 1](#).

**Table 1 Changes to Protocol Defined Analysis Plan**

Protocol	Reporting & Analysis Plan	
Statistical Analysis Plan	Statistical Analysis Plan	Rationale for Changes

 
Part A (single dose): Dose proportionality will be assessed by visual inspection of dose normalised AUC(0-∞) [or if not available AUC(0-t)] and Cmax values versus dose. Analysis of these loge-transformed parameters may be carried out, using the power model.
 
	
 
Summary of dose normalised PK parameters will be replaced by summary of PK parameters
 
No analyses of log-transformed data will be conducted
 
	
 
Study terminated prior to full dose escalation completion
 

 
Part A (food effect): The ratio of fed state to fasted state may be assessed for the loge-transformed parameters AUC(0-∞) [or if not available AUC(0-t)] and Cmax. The effect of food will be assessed utilising a mixed effects model, with fed state (fasted or fed) as a fixed effect and participant as a random effect
 
	
 
No food effect summaries or statistical analyses
 
	
 
Study terminated prior to fed dosing period
 

 
Part B: The extent of accumulation after repeat
 
	
 
No Part B summaries or statistical analyses
 
	
 
Study terminated prior to Part B multiple ascending
 

Protocol	Reporting & Analysis Plan	
Statistical Analysis Plan	Statistical Analysis Plan	Rationale for Changes
dosing, the observed accumulation ratio (Ro), may be determined. The plasma steady state ratio (Rs) and an assessment of plasma steady state across the trough concentrations may also be made. Dose proportionality may be assessed using similar methods to the single dose Part A.		dose cohorts

 
For combined 5-ABT and NAc-5-ABT (corrected to 5-ABT), observed Cmax and Tmax will be determined using non-compartmental methods and will be summarised descriptively
 
	
 
5-ABT and NAc-5-ABT (corrected to 5-ABT) concentrations will be listed. No PK parameters will be produced
 
	
 
Limited number of subjects with quantifiable 5-ABT and NAc-5-ABT PK concentrations to warrant summaries or PK parameter derivations
 

 
To investigate the metabolic profile of GSK2983559 following single and/or repeat doses in healthy participants in urine
 
	
 
No urine data will be reported
 
	
 
Data is no longer planned due to study termination prior to urine samples being analysed
 

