#### **5.5.5. Assessment and control of 5-ABT**

5-amino-benzothiazole (5-ABT), an impurity in the GSK2983559 drug substance (3-6 parts per million (ppm) [m.2.1.S.3.2 Impurities in chemistry, manufacturing and controls (CMC) investigational medicinal product dossier (IMPD)], was found to be mutagenic in an in vitro Ames assay. In addition, 5-ABT was formed from GSK2668176 in bio relevant media (pH 6.5 and pH 8 in FaSSIF and FeSSIF conditions), suggesting that a theoretical risk exists for its formation at physiological pH. According to ICH M7 guidance for the assessment and control of deoxyribonucleic acid (DNA) reactive (mutagenic) impurities in pharmaceuticals to limit potential carcinogenic risk, 5-ABT is classified as a Class 2 hazard (i.e. known mutagen with unknown carcinogenic potential) and must be controlled at or below the Threshold of Toxicological Concern (TTC) of 120  $\mu\text{g}/\text{day}$  considering the duration of treatment of  $\leq 1$  month..

5-ABT is not predicted to be a metabolite, and has not been observed as a metabolite in in vitro hepatocyte or S9 incubations. Real time analysis of plasma samples from FTIH for 5-ABT and its metabolite N-acetyl 5-ABT will be performed to monitor exposure to 5-ABT in healthy volunteers.

Quantifiable concentrations of 5-ABT were observed below the stopping criteria (combined  $C_{max}$  of 5-ABT and NAc-5-ABT of 3 ng/mL) in 4 out of 8 subjects treated with GSK2983559 in Cohort 1 at the 100-mg dose level. The maximum observed 5-ABT concentration was 1.25 ng/mL. An enteric capsule [Hydroxypropylmethyl Cellulose Acetate Succinate (HPMCAS)] will be used starting in Cohort 2 and carry through to Cohort 6 to determine if this formulation will minimize the gastric conversion of drug substance to 5-ABT. The disintegration of an enteric capsule is pH dependent and is expected to avoid hydrolysis of the active pharmaceutical ingredient (API) to 5-ABT in the acidic environment of the stomach and release API in a higher pH environment in the proximal small intestine.

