### 8.2. PK criteria for 5-ABT and NAc-5-ABT

The drug product contains an impurity (5-ABT) known to be mutagenic (with unknown carcinogenic potential) that is controlled in drug production to assure its level is below a Threshold of Toxicological Concern (TTC) per the ICH M7 guideline. However, because of a possibility for 5-ABT to be formed in the body, monitoring for 5-ABT (and its metabolite, NAc-5-ABT) in blood plasma will be undertaken with application of the

same TTC (120 µg), which translates to a plasma concentration of 3 ng/mL under the assumption that the mutagenic impurity distributes into a volume equal to total body water of 42L. Based on this information, if in any individual the Cmax of combined concentration of 5-ABT and NAc-5-ABT (in ng/mL equivalents 5-ABT/mL) is > 3 ng/mL, it will suggest the TTC level of 120 µg has been reached and further dose-escalation will be stopped. During dose escalation, progression to the next dose level will be guided by the criteria where the maximum predicted 5-ABT amount for the next dose will not exceed the TTC of 120 µg.

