### 11.3.2. PK Analyses

All pharmacokinetic analyses will be performed on the Pharmacokinetic Population.

For the secondary pharmacokinetic (PK) endpoints in this study, no formal hypotheses will be tested.

Endpoint	Statistical Analysis Methods
Secondary	
Plasma GSK2983559 and GSK2668176, concentration-time data will be analysed by non-compartmental methods. Calculations will be based on the actual sampling times recorded during the study.
 
From the plasma concentration-time data, the following pharmacokinetic parameters will be determined, as data permit: maximum observed plasma concentration (<math>C_{max}</math>), time to <math>C_{max}</math> (<math>t_{max}</math>), area under the plasma concentration-time curve [<math>AUC_{(0-24)}</math>, <math>AUC_{(0-t)}</math> and <math>AUC_{(0-\infty)}</math>], and apparent terminal phase half-life (<math>t_{1/2}</math>).
 
Part A (single dose): Dose proportionality will be assessed by visual inspection of dose normalised <math>AUC_{(0-\infty)}</math> [or if not available <math>AUC_{(0-t)}</math>] and <math>C_{max}</math> values versus dose. Analysis of these <math>\log_e</math>-transformed parameters may be carried out, using the power model.
 
Part A (food effect): The ratio of fed state to fasted state may be assessed for the <math>\log_e</math>-transformed parameters <math>AUC_{(0-\infty)}</math> [or if not available <math>AUC_{(0-t)}</math>] and <math>C_{max}</math>. The effect of food will be assessed utilising a mixed effects model, with fed state (fasted or fed) as a fixed effect and participant as a random effect.
 
Part B: The extent of accumulation after repeat dosing, the observed accumulation ratio (<math>R_o</math>), may be determined. The plasma steady state ratio (<math>R_s</math>) and an assessment of plasma steady state across the trough concentrations may also be made. Dose proportionality may be assessed using similar methods to the single dose Part A.
 
For combined 5-ABT and NAc-5-ABT (corrected to 5-ABT), observed <math>C_{max}</math> and <math>T_{max}</math> will be determined using non-compartmental methods and will be summarised descriptively.
 
Further details will be included in the RAP.

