
 
To assess the effect of food on the pharmacokinetics of GSK2983559 and its active moiety GSK2668176 in fasted and fed state in healthy participants.
 
	
 
Derived PK parameters for GSK2983559, and GSK2668176 including area under the plasma drug concentration versus time curve (AUC(0-t), AUC(0-∞)), maximum observed plasma drug concentration (Cmax), time to maximum observed plasma drug concentration (tmax), and terminal half-life (t1/2) following single (fed and fasted) dose, where data allow.
 

Exploratory Objectives	Exploratory Endpoints

 
To determine the PD effect of single and repeat doses of GSK2983559 in healthy participants.
 
	
 
PD/biomarker endpoints may include, but not be limited to, assessments of pharmacologic effects through measurements of target engagement and pathway activation. These may include measurements of RIP-2 receptor occupancy, and levels of MIP1<math>\alpha</math>, MIP1<math>\beta</math> and TNF proteins, following stimulation of whole blood, as data permit. (Cohort 1 subjects only)
 

 
To investigate the metabolic profile of GSK2983559 following single and/or repeat doses in healthy participants in blood and urine
 
	
 
Identification and quantitative estimates of GSK2983559 and its active moiety GSK2668176 and potential metabolites following single and repeat doses in plasma and urine.
 

 
To characterize exposure to 5-ABT and NAc-5-ABT after single and repeated doses of GSK2983559 in healthy participants.
 
	
 
Concentration of 5-ABT and NAc-5-ABT (adjusted to 5-ABT concentration based on molecular weight (MW)) and derive Cmax for the combined concentration curve of 5-ABT and MW adjusted NAc-5-ABT
 

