### 11.10.12. Non-ICH Listings

Non-ICH: Listings					
No.	Population	IDSL / Example Shell	Title	Programming Notes	Deliverable [Priority]
Pharmacokinetic					
31.	Pharmacokinetic	PK08	Listing of Plasma GSK2983559 Pharmacokinetic Concentration-Time Data: Part A		SAC
32.	Pharmacokinetic	PK08	Listing of Plasma GSK2668176 Pharmacokinetic Concentration-Time Data: Part A		SAC
33.	Pharmacokinetic	PK08	Listing of Plasma 5-ABT Pharmacokinetic Concentration-Time Data: Part A		SAC
34.	Pharmacokinetic	PK08	Listing of Plasma NAc-5-ABT Pharmacokinetic Concentration-Time Data: Part A		SAC
Pharmacodynamic					
35.	Safety		Listing of Pathway Activation Markers	TNF $\alpha$ , MIP-1 $\alpha$ , MIP-1 $\beta$	SAC

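### The SAP replaces the combined 5-ABT + NAc-5-ABT Cmax with two single-analyte listings, so no display shown gives the value that the 3 ng/mL escalation stop acts on

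*SAP*

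**What the plan says.** Protocol section 4 lists, as an exploratory endpoint, the Cmax "for the combined concentration curve of 5-ABT and MW adjusted NAc-5-ABT"; SAP 2.2 repeats it. Protocol 11.3.2 plans a descriptive summary of the combined Cmax and Tmax. Protocol 8.2 uses the same quantity as a stop: if the combined Cmax in any individual "is > 3 ng/mL, it will suggest the TTC level of 120 µg has been reached and further dose-escalation will be stopped".

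SAP Table 1 (section 2.1) replaces the planned summary: "5-ABT and NAc-5-ABT (corrected to 5-ABT) concentrations will be listed. No PK parameters will be produced". The rationale is "Limited number of subjects with quantifiable 5-ABT and NAc-5-ABT PK concentrations to warrant summaries or PK parameter derivations". SAP 8.1.1 and 8.2 repeat that these concentrations are only listed.

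The matching displays in SAP 11.10.12 are Listing 33 (5-ABT) and Listing 34, "Listing of Plasma NAc-5-ABT Pharmacokinetic Concentration-Time Data: Part A". The PK tables and figures in SAP 11.10.7 and 11.10.8 cover only the prodrug and its active moiety. SAP 11.5.2 keeps participant-level listings out of the main body of the report, and SAP 11.5.3 limits imputation of concentrations to summaries and summary figures.

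Protocol 5.5.5 reports that quantifiable 5-ABT was seen "in 4 out of 8 subjects treated with GSK2983559 in Cohort 1 at the 100-mg dose level", with a maximum of 1.25 ng/mL. It says the enteric capsule was introduced "to determine if this formulation will minimize the gastric conversion of drug substance to 5-ABT".

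**The concern.** The stop acts on a sum within one person. The planned displays show the two parts in separate listings and nowhere show the sum, its maximum, or how many participants exceeded 3 ng/mL. The study has an explicit objective to characterise exposure to this mutagenic degradant. With no table planned, the displays shown would put no 5-ABT result in the body of the report.

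The stated rationale does not fit what was dropped. Sparse quantifiable data make means, standard deviations and half-lives uninformative. An observed maximum needs only one quantifiable value, and a count of quantifiable participants is informative even when it is zero.

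**Working it through.** **1. The plan's threshold.** Protocol 8.2 gives a threshold of toxicological concern of 120 µg and a volume of 42 L.

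- 120 µg / 42 L = 2.857 ng/mL, which rounds to the stated 3 ng/mL.
- In reverse, 3 ng/mL × 42 L = 126 µg, 5% above 120 µg. The figure is reproduced up to rounding.

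**2. What the stop needs.** For each participant and dose:

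combined Cmax = maximum over sampling times of [5-ABT + adjusted NAc-5-ABT].

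Neither analyte alone settles whether this exceeds 3 ng/mL. With illustrative values of 1.6 ng/mL for each analyte at the same time, 1.6 + 1.6 = 3.2 ng/mL. That is above the stop, although both listings show values below 3. The 1.25 ng/mL maximum in Protocol 5.5.5 is for 5-ABT alone. It leaves 3 − 1.25 = 1.75 ng/mL (5-ABT equivalents) for the metabolite before the stop is exceeded.

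**3. Whether the question is live at the doses given.** SAP 2.1 says Cohort 2 received two of its four planned doses, and SAP 5.1 shows these as 200 and 400 mg enteric. Assume that the 100 mg maximum scales linearly with dose and that the capsule has no effect:

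- 200 mg: 1.25 × 2 = 2.5 ng/mL
- 400 mg: 1.25 × 4 = 5.0 ng/mL
- 3 ng/mL is reached at 100 × 3 / 1.25 = 240 mg

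These are illustrations for 5-ABT alone. The documents give no Cohort 2 results.

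**4. The NQ gap.** Suppose one analyte is quantified at q and the other is NQ with assay limit L, in 5-ABT equivalents. The sum then lies between q and q + L, so its position against the stop is unclear when 3 − L < q ≤ 3. The documents give no assay limit for either analyte; the 0.20 ng/mL in Protocol 5.4 is for GSK2668176. The imputation standard named in SAP 11.5.3 is not applied to listings.

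**5. The rationale.** At 100 mg, 4 of 8 participants on active had quantifiable 5-ABT (exact 95% interval 0.16 to 0.84). This concerns one analyte at one dose. It shows that there are individual maxima to report. It does not show that the rationale is false across Part A.

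**6. The two capsules.** Standard: 2, 4, 10, 30 and 100 mg in Cohort 1. Enteric: 200 and 400 mg in Cohort 2. No dose and no participant is shared. An illustrative enteric maximum of 2.0 ng/mL at 400 mg is higher than 1.25 at 100 mg in raw terms. Per mg it is 1 − 2.0/5.0 = 60% lower, but only if formation of 5-ABT is linear in dose.

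**The case against.** The strongest reply is that nothing is withheld. Both analytes are listed by participant and time, and SAP 8.1.1 and 8.2 say that NAc-5-ABT is expressed in 5-ABT equivalents. Table 1 declares the change and gives a reason, the endpoint is exploratory, and the study was terminated with no formal hypotheses. All of this stands and limits the point.

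A reader might infer four stronger things that the documents do not support:

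- **That the report cannot show whether anyone crossed the stop.** It can be worked out by adding Listings 33 and 34, apart from time points left unclear by an NQ value. The report does not display it.
- **That the stop went unmonitored.** Protocol 5.5.5 and Appendix 3 provide for real-time analysis and committee review of both analytes. SAP 3.1 says the committee's decisions after each Part A period drew on 5-ABT concentrations. The gap is in reporting.
- **That the SAP contradicts itself because section 2.2 keeps the endpoint.** Section 2.2 restates the protocol's objectives, including the repeat-dose, food-effect and urine items that Table 1 also drops. Table 1 is where departures are declared.
- **That dropping Cmax lost a capsule comparison.** None was a planned analysis. The formulation question is the amendment's rationale, and capsule is confounded with dose and cohort whatever is tabulated.

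One uncertainty remains. SAP 11.10.1 numbers listings to 37, but only 31 to 35 appear, so the point is limited to the displays shown.

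**Conclusion.** The point holds as a reporting gap. No display shown gives the combined Cmax, a flag against 3 ng/mL, or a count of participants with quantifiable values, and no rule is stated for adding the analytes when one is NQ. A limited number of quantifiable participants supports dropping means and modelled parameters. It does not support dropping an individual observed maximum or a count.

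The effect on this trial cannot be sized, because the Cohort 2 and NAc-5-ABT results are not in the documents. The 3.2, 2.5 and 5.0 ng/mL figures show only that the sum can matter and that the question is real at 200 and 400 mg, under the assumptions stated. No conclusion about the enteric capsule follows in either direction. The change should still be made: it is nearly free and lets the report answer its own exposure objective.

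**What to change.** 1. Add to the 5-ABT listings a combined concentration (5-ABT plus adjusted NAc-5-ABT) at each time point, with a stated rule for when one or both analytes are NQ. Say in the title of Listing 34 that its values are in 5-ABT equivalents.
2. List the observed combined Cmax per participant and dose, flagged if above 3 ng/mL.
3. Add one descriptive table by dose, each dose labelled with its capsule type: n dosed, n with any quantifiable value, maximum combined Cmax, and n above 3 ng/mL. A maximum per 100 mg is optional and should carry a note that it assumes dose-linearity. State that any reading of standard against enteric is descriptive only.
4. Revise the Table 1 row to match: individual observed maxima and counts are reported; means and other derived parameters are not.

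The cost is some added listing columns and one small table, from concentrations already measured and with no modelling. The downside is that many entries may be NQ at low doses.
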